10.3.2.3 Safety Population

All subjects who received at least one dose of investigational product. Treatment classification will be based on the actual treatment received. This will be primary population for the safety analyses.

10.3.3 Analysis Windows and Baseline

The observational period for the study includes the screening period (Day -28 to Day -1), the treatment period (Day 1 to Day 690), and the EOS visit (Day 720±3 weeks). Any event occurring beyond the defined observational period, even if collected on the eCRF, will not be included in the planned statistical analysis. However, all data, including that reported after the defined observational period, will be included in the subject data listings.

Unless otherwise specified, for evaluations that are collected at multiple occasions prior to initiation of investigational product administration, the latest evaluation will be considered the "Baseline" evaluation for analysis.

10.3.4 Missing Data Handling

The sponsor will diligently follow up each subject from the beginning till end of study (Day 720±3 weeks), and make every effort to keep each subject visit within protocol specified window on all efficacy assessments of lipids/lipoproteins/biomarkers to keep missing data to the minimum

regardless of whether the subject is on study treatment, use ancillary therapies, experience an adverse event, or adhere to the protocol.

However, if a missing value indeed occurs for any efficacy parameter up to Day 180, it's going to be imputed using appropriate imputation method. The method of the imputation will be consistent with that in the other Phase III studies and the details will be in the SAP.

For all missing values after Day 180 on all efficacy parameters, for all other parameters other than efficacy, missing data will not be imputed and will be excluded from the associated analysis.

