HoFH	homozygous familial hypercholesterolemia
HR	heart rate
hsCRP	high sensitivity C-reactive protein
IB	Investigator's Brochure
ICH	International Conference on Harmonisation of Technical Requirements for Registration of Pharmaceuticals
IDMC	Independent Data Monitoring Committee
IFN- γ	interferon-gamma
IL6	interleukin 6
INR	International normalized ratio
IRB	Institutional Review Board
IRT	Interactive Response Technology
ITT	intent-to-treat
IV	Intravenous
L	Liter(s)
LDL	low density lipoprotein
LDL-C	low density lipoprotein cholesterol
LDLR	low density lipoprotein receptor
Lp(a)	lipoprotein(a)
<hr/>	
MCH	mean cell hemoglobin
MCHC	mean corpuscular hemoglobin concentration
MCV	mean corpuscular volume
MDCO	The Medicines Company
MedDRA	Medical Dictionary for Regulatory Activities
mg	Milligram
MI	myocardial infarction
MITT	Modified intent-to-treat
mL	milliliter(s)
mmHg	millimeters of mercury
mmol	Millimole
MMRM	mixed-effect models for repeated measures
mRNA	messenger ribonucleic acid
NYHA	New York Heart Association
PCS	potentially clinical significant
PCSK9	proprotein convertase subtilisin/kexin type 9
PD	pharmacodynamic
PEF	peak expiratory flow
PK	pharmacokinetic
PMM	Pattern-Mixture Model

PT	prothrombin time
RISC	RNA-induced silencing complex
RNA	ribonucleic acid
RNAi	ribonucleic acid interference
SAE	serious adverse event
SAP	Statistical Analysis Plan
SC	Subcutaneous
SD	standard deviation
siRNA	small interfering ribonucleic acid
SUSAR	suspected unexpected serious adverse reaction
$t_{1/2}$	terminal half-life
TBIL	total bilirubin
TC	total cholesterol
TEAE	treatment emergent adverse event
TNF- α	tumor necrosis factor-alpha
TTR	target transthyretin
ULN	upper limit of normal
US	United States
VLDL-C	very low density lipoprotein cholesterol
WHO	World Health Organization

Amendment 1 (08-Oct-2020)

Amendment rationale

The first subject for this trial was randomized in Feb 2019 and enrollment was completed in Sep 2019 (with 56 subjects enrolled). Part 1 (double-blind phase) of the trial was completed on 02-Mar-2020, when the last subject completed the Day 180 visit and treatment allocation was unblinded. At time of this amendment, 51 subjects are still on study treatment.

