3.4 Secondary Endpoints

[figure not shown]
The key secondary endpoints of this study are:

- Absolute change in LDL-C from baseline to Day 150
- Percentage change in Apo-B from baseline to Day 150.
- Percentage change in non-HDL-C from baseline to Day 150.
- Percentage change in total cholesterol from baseline to Day 150.
- Proportion of subjects in each group with $\geq 30\%$ LDL-C reduction from baseline at Day 150.

The other secondary endpoints of this study are:

- Percentage change and absolute change in LDL-C from baseline to each assessment time up to Day 720 (ie, Days 90, 150, 180, 270, 330, 450, 510, 630, 690, and 720)
- Percentage change and absolute change from baseline to Days 90, 150, 180, 330, 510, 690, and 720 in PCSK9
- Percentage change and absolute change from baseline to Days 150, 180, 330, 510, 690, and 720 in total cholesterol, Apo-B, and non-HDL-C for subjects receiving inclisiran
- Individual responsiveness of subjects defined as the number of subjects reaching on treatment LDL-C levels of <25 mg/dL, <50 mg/dL, <70 mg/dL, and <100 mg/dL at Days 150, 180, 330, 510, 690, and 720 including proportion of subjects in each group who attain global lipid targets for their indication
- Proportion of subjects in each group with greater or equal to 30% LDL-C reduction from baseline at Days 150, 180, 330, 510, 690, and 720

- Absolute change and percentage change in other lipids, lipoproteins, apolipoproteins, and PCSK9 from baseline at each subsequent visit to Day 720
- Safety and tolerability profile of inclisiran as measured by AEs, SAEs, vital signs, clinical laboratory values, ECG measurements and formation and subsequent characterization of anti-drug antibodies (ADA)

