4.4 Withdrawal Criteria

All subjects have the right to withdraw from the study at any point during treatment without prejudice. The investigator can discontinue any subject at any time if medically necessary. It will be documented whether or not each subject completed the clinical study. If study treatment or observations were discontinued, the reason will be recorded and the Sponsor should be notified promptly. The reasons a subject may discontinue their participation in the study could be from one of the following:

- AE
- Death
- Subject withdrew consent
- Physician decision
- Lost to follow-up
- Initiation of protocol-prohibited lipid-lowering therapy (eg, an approved PCSK9 inhibitor)

The applicable reason above will be recorded in the eCRF. All data collected up until the time of subject withdrawal is to be entered into the eCRF. All subjects discontinuing participation in this trial should be encouraged to complete the EOS visit except for those subjects who specifically withdrew consent.

Participating study sites will be trained on the importance of completing study follow-up procedures, and collecting the documentation required for missing data values. Any withdrawn subjects will not be replaced in this study.

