10.4.3.2 Secondary Efficacy Endpoints

For the first four key secondary endpoints, the following efficacy analyses will be performed on the ITT and mITT populations:

- Similar to the primary analysis of the primary efficacy endpoint, the ANCOVA model will be used on the multiply imputed datasets (100 total) – Washout based approach. Treatment effects from these 100 ANCOVA analyses will then be combined using Rubin's method.
- MMRM model will be used on the multiply imputed datasets (100 total) – PPM based imputation. Treatment effects from these 100 ANCOVA analyses will then be combined using Rubin's method
- Analysis based on a Mixed-effects Model for Repeated Measures (MMRM) without multiple imputation will be performed.

For the key secondary endpoint of $\geq 30\%$ LDL-C reduction from baseline to Day 150, a logistic regression model with treatment as the effect will be used, and the odds ratio and its 95% confidence interval will be provided. The multiply imputed datasets created from both the washout model and the control-based PMM will be utilized in this analysis.

For the other secondary endpoints specified in [Section 3.4](#), generally descriptive and graphical summaries by treatment group will be presented for the ITT population. The two-sided 95% confidence interval may be provided for continuous variables based on the MMRM model. Odds ratio and 95% confidence interval may be provided for binary variables. Nominal p-values may be provided when applicable. Details of the analyses for the secondary endpoints are specified in the SAP.

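### Responder proportions move from imputed data at Days 150 and 180 to available cases from Day 330, so later rates rest on a different basis and could be overstated

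*Protocol*

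**What the plan says.** Protocol Section 10.3.4 has two rules. Up to Day 180, "if a missing value indeed occurs for any efficacy parameter up to Day 180, it's going to be imputed using appropriate imputation method", with the method left to the SAP. After Day 180, for all efficacy parameters, "missing data will not be imputed and will be excluded from the associated analysis". The second rule is fixed in the protocol itself.

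Section 3.4 defines endpoints that cross the boundary. One is the proportion with "greater or equal to 30% LDL-C reduction from baseline at Days 150, 180, 330, 510, 690, and 720". Another, at the same visits, includes the "proportion of subjects in each group who attain global lipid targets for their indication". For the Day 150 responder analysis, Section 10.4.3.2 specifies logistic regression and adds: "The multiply imputed datasets created from both the washout model and the control-based PMM will be utilized in this analysis". The same section presents the other secondary endpoints for the ITT population, which Section 10.3.2.1 defines as everyone randomized.

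Section 4.4 lists among the reasons for leaving the study: "Initiation of protocol-prohibited lipid-lowering therapy (eg, an approved PCSK9 inhibitor". Subjects who leave are encouraged to attend an end-of-study visit, unless they withdrew consent. On numbers, the amendment rationale reports 56 enrolled and states: "At time of this amendment, 51 subjects are still on study treatment".

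**The concern.** A responder proportion followed over time is read as evidence of durability, and Part 2 has no concurrent control to set it against. Here the series is built on imputed data at Days 150 and 180 and on whoever supplies a value from Day 330. The denominator can shrink as subjects leave. The plan names the ITT population for these summaries but states no denominator that would reconcile that with the exclusion.

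One listed exit is plausibly related to response. Section 5.2.1 bars adding or changing lipid-lowering treatment, so a subject who needs more LDL-C lowering must deviate or leave. Non-response is not hypothetical in this disease: Section 1.2.2.2.3 describes a four-subject pilot in which one subject's PCSK9 fell without a matching fall in LDL-C. An end-of-study visit cannot supply missed Day 330, 510 or 690 values. If those who leave respond less often, the observed proportion could hold steady or rise although no individual's LDL-C improved.

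**Working it through.** The protocol gives no figure on this point to reproduce: no Part 2 response rate and no count of missing LDL-C. Its power statement in Section 10.1 does not depend on this rule. What follows is therefore a range under stated assumptions.

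**Which rule applies at which visit (Sections 3.4 and 10.3.4)**

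| Visit | Rule for missing values |
|---|---|
| Days 150, 180 | Imputed |
| Days 330, 510, 690, 720 | Excluded |

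**Inputs**

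- N = 56 enrolled and 51 still on treatment (amendment rationale), so 56 − 51 = 5 off treatment.
- Assumption: m = 5 subjects have missing LDL-C; m = 10 as a second case. Being off treatment is not the same as having no LDL-C value, so m = 5 is an illustration only.
- Assumption: observed-case rate r between 20% and 80%.
- q = response rate among the missing subjects, unknown.

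**Formula.** The full-denominator rate is [r(N − m) + qm]/N. The observed-case rate exceeds it by (r − q)·m/N. With q = 0 this is r·m/N.

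**Results if no missing subject responds (q = 0)**

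| Observed rate | Full rate, 5 of 56 missing | Excess (points) | Full rate, 10 of 56 missing | Excess (points) |
|---|---|---|---|---|
| 20% | 18.2% | 1.8 | 16.4% | 3.6 |
| 30% | 27.3% | 2.7 | 24.6% | 5.4 |
| 50% | 45.5% | 4.5 | 41.1% | 8.9 |
| 80% | 72.9% | 7.1 | 65.7% | 14.3 |

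For example, 0.80 × 5/56 = 0.071 and 0.80 × 10/56 = 0.143.

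**Other values of q.** If q = r, the excess is zero. If every missing subject would have responded (q = 1), the observed rate is too low by (1 − r)·m/N. With m = 5 that is 0.80 × 5/56 = 7.1 points at r = 20% and 0.20 × 5/56 = 1.8 points at r = 80%.

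**By group.** The endpoint is reported by group, and the split of the 56 is not given. Assuming 37 and 19 from the 2:1 allocation, with all 5 missing in one group and q = 0, the excess is r × 5/37 = 2.7 to 10.8 points in the inclisiran group, or r × 5/19 = 5.3 to 21.1 points in the former placebo group. These are extreme cases.

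**The case against.** A reader might infer that the long-term rates are inflated. The documents do not show that. Upward bias needs q < r, and nothing states that poor responders leave more often or that sites see LDL-C results in Part 2. Section 6.1 lets remote contacts replace clinic visits during the pandemic, which can cause missing values unrelated to response.

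The plan also intends to limit missingness. Section 10.3.4 opens by calling for efficacy follow-up to Day 720 whatever the subject's treatment, ancillary therapy or adherence, and Section 4.5.1 asks subjects permanently off drug to complete the remaining visits. Stopping inclisiran should not by itself produce a missing value. This stands. The gap is confined to those who leave the study.

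The 56-based arithmetic is pooled, whereas reporting is by group, and the protocol does not say when the 5 went off treatment. Had all 5 left the study before Part 2, they would not be in a denominator of Part 2 entrants and would contribute no gap. The figures are therefore a scale, not an estimate.

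Scope is also limited. The LDL-C threshold endpoint is worded first as a number of subjects, and excluding missing subjects cannot raise a count. Some change of rule follows from the design: once everyone receives inclisiran there is no concurrent placebo arm for control-based imputation. In the former placebo group, Day 150 and later visits compare different treatments whatever the missing-data rule.

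Finally, scoring every subject who stops inclisiran as a non-responder would override measured LDL-C and impose a debatable estimand. That objection succeeds, and the fix below does not do it. What remains is that the protocol itself fixes the exclusion rule, so leaving details of the secondary analyses to the SAP does not answer the point.

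**Conclusion.** The point holds as a cheap improvement. The ≥30% responder proportion and the lipid-target proportion change their missing-data basis between Day 180 and Day 330, so the later rates are not on the same footing as the Day 150 rate. They could also be overstated if study leavers respond less often than those observed.

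The direction and size are not established. The 1.8 to 7.1 points (5 missing) and 3.6 to 14.3 points (10 missing) rest on assumed counts of missing LDL-C, assumed observed rates of 20% to 80%, and no response among the missing. The documents do not support reading this as a threat to the trial's conclusions: the synopsis limits statistical comparisons to Part 1 and makes Part 2 descriptive. What is at stake is how fairly durability is described.

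**What to change.** In Section 10.3.4, for binary efficacy endpoints after Day 180:

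- Keep the observed-case proportion.
- Show beside it, by randomized group, a supplementary proportion whose denominator is all subjects of that group who entered Part 2, less the exclusions in the next item but one.
- In that line, count subjects whose LDL-C is missing because they left the study as non-responders.
- Continue to exclude visits missed for pandemic or administrative reasons by subjects still in the study.
- Use measured LDL-C as measured, including after inclisiran is stopped. Flag values taken after the start of prohibited lipid-lowering therapy and count them as non-response in the supplementary line only; otherwise a subject who starts such therapy and stays could appear as a responder to inclisiran.
- Report the number missing by visit and group.

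The cost is a short addition to Section 10.3.4 and one extra line per table. The supplementary long-term rates will look somewhat less favourable than the observed-case ones.

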10.4 Statistical Analyses

10.4.1 Demographic and Background Characteristics

Subject demographics and baseline characteristics (including medical history) will be summarized by treatment group using the ITT or safety populations.

10.4.2 Investigational Product and Concomitant Medications

Summaries of investigational product and each prior (pre-baseline) medication and concomitant (baseline or later) medication will be provided by treatment. Separate summaries will be provided for prior medication use. Medications will be coded using the World Health Organization (WHO) drug dictionary. Subjects will be counted only once within each period by medication.

10.4.3 Efficacy Analysis

This study is sufficiently powered to show the effect in the primary and key secondary endpoints, all other secondary [REDACTED] endpoints are supportive hence statistical testing on all other secondary [REDACTED] endpoints will be performed only if the null hypothesis on primary and the key secondary endpoints are rejected. No adjustment for multiplicity is planned among the other secondary [REDACTED] endpoints.

The ITT population will be the primary population for the efficacy analysis. Efficacy analysis may also be performed for the mITT population as supportive analysis.

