Unless specified otherwise, the ITT will be the primary analysis population for efficacy analysis and Safety population will be the primary population for safety analysis in this study. mITT population will be used to confirm the efficacy.

Statistical Analysis:

Statistical comparisons will only be performed for the Part 1 of the study. The statistical analysis for study Part 2 is descriptive.

Summary statistics for continuous variables will include the number of subjects, mean, median, standard deviation or standard error, minimum and maximum. For categorical variables, the frequency and percentage will be given.

The primary endpoint is the percent change from baseline in LDL-C following 150 days of treatment.

The primary analysis will be conducted using ANCOVA model based on the multiply imputed datasets (100 total) - Washout based approach. The ANCOVA model will include the fixed effect of treatment group (Inclisiran or placebo) and baseline LDL-C as a covariate. Treatment effects from these 100 ANCOVA analyses will then be combined using Rubin's method. The difference between treatment groups in mean change from baseline to Day 150 in LDL-C and corresponding two-sided 95% confidence interval will be provided. The p value for testing equal mean change from baseline to Day 150 in LDL-C will also be provided. For the key secondary endpoints, the efficacy analyses will be similar to the primary analysis of the primary efficacy endpoint, the ANCOVA model will be used on the multiply imputed datasets (100 total) - Washout based approach. Treatment effects from these 100 ANCOVA analyses will then be combined using Rubin's method.

Additionally sensitivity analysis including MMRM on imputed data using PMM and without imputation will be performed for both primary and key secondary endpoints except for the endpoint of $\geq 30\%$ LDL-C reduction from baseline to Day 150, which will be analyzed using the logistic regression model with treatment as the effect.

This study is sufficiently powered for the hypothesis testing in the primary and key secondary endpoints, all other endpoints are supportive hence no adjustment for multiplicity is planned.

Safety summaries will include the incidence of AEs, summaries of laboratory parameters, vital signs, and ECGs.

Table of contents

Protocol Synopsis	2
Table of contents.....	8
List of tables.....	12
List of figures.....	12
List of abbreviations	13
Amendment 1 (08-Oct-2020).....	16
1 Introduction.....	26

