10.1 Sample Size

The sample size calculation was performed with the hypothesis that the difference of mean percent change from baseline to Day 150 between inclisiran and placebo will be >20% (20% standard deviation) in subjects with HoFH when treated with inclisiran. The sample size of at least 45 subjects (randomized 2:1 to inclisiran : placebo), with at least 30 subjects in the inclisiran arm, will provide >80% power to detect a 20% reduction of LDL-C levels from baseline in the inclisiran group compared to that in the placebo at one-sided significance level of 0.025 based on two-sample t-test.

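### The claim of sufficient power for the key secondary endpoints fails for the ≥30% LDL-C responder endpoint, which has about 39–54% power at N=45 under the protocol's own 20/20 planning assumption

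*Protocol*

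**What the plan says.** Section 10.4.3 says "This study is sufficiently powered to show the effect in the primary and key secondary endpoints". The Statistical Analysis part of the synopsis says "This study is sufficiently powered for the hypothesis testing in the primary and key secondary endpoints".

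Section 3.4 lists five key secondary endpoints at Day 150. Four are continuous. The fifth is the proportion of subjects with an LDL-C reduction of 30% or more. For that endpoint section 10.4.3.2 says "a logistic regression model with treatment as the effect will be used", with an odds ratio and 95% confidence interval from the multiply imputed datasets.

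The only power calculation is in section 10.1, and the synopsis repeats it. It hypothesises that "the difference of mean percent change from baseline to Day 150 between inclisiran and placebo will be >20% (20% standard deviation"). It sets at least 45 subjects at 2:1 with at least 30 on inclisiran, and claims more than 80% power "at one-sided significance level of 0.025 based on two-sample t-test". No responder rate, effect size or power is given for any key secondary endpoint.

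Section 10.4.3 adds that testing of the other secondary endpoints "will be performed only if the null hypothesis on primary and the key secondary endpoints are rejected".

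**The concern.** Cutting a continuous outcome at a threshold usually loses power. Here the threshold, a 30% reduction, lies beyond the planned inclisiran mean of about 20%, so most treated subjects would be non-responders even if the drug worked as planned. A trial sized for the mean difference cannot be assumed to have enough subjects for the responder comparison, yet the protocol says that it does.

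Two things are at stake. First, a non-significant responder result could be taken as the failure of an adequately powered endpoint when it is close to a coin toss under the planning values. Second, because section 10.4.3 makes testing of the other secondary endpoints depend on the key secondary nulls, this endpoint limits how often that gate opens. Nothing in the protocol makes the primary or the other four key secondaries depend on it.

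**Working it through.** **Inputs**
- Difference 20 points, SD 20, 30 vs 15, one-sided 0.025: section 10.1.
- Inclisiran mean about −20%: the synopsis hypothesis of a mean change beyond 20% from Day 1. With a 20-point difference this implies a placebo mean of 0, which is inferred and not stated.
- Normally distributed percent changes: assumed.
- 56 enrolled: Amendment 1 rationale. The 37/19 split is assumed from 2:1.
- No dropout is applied, because none is stated.

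**Step 1. Reproduce the plan's own figure (primary endpoint).**
Noncentrality = 20 / (20·√(1/30 + 1/15)) = 1/√0.1 = 3.16, with 30 + 15 − 2 = 43 degrees of freedom. The noncentral t gives power of 87.1%, so the claim of more than 80% holds. At 37/19 it is 93.6%.

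**Step 2. Responder rates implied by the same assumption.**
- Inclisiran: Φ((−30 + 20)/20) = Φ(−0.5) = 30.9%
- Placebo: Φ((−30 − 0)/20) = Φ(−1.5) = 6.7%

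**Step 3. Power for 30.9% vs 6.7%.** All two-by-two outcomes were enumerated, weighted by their binomial probabilities, and counted as rejections at two-sided 0.05 in the direction of benefit.

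| Test | 30/15 | 37/19 |
|---|---|---|
| Fisher exact | 39.2% | 51.1% |
| Score chi-square | 49.8% | 57.5% |
| Likelihood ratio (logistic) | 53.9% | 63.0% |
| Wald (logistic) | 8.1% | 23.6% |

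The Wald figure is low because tables with no placebo responder were counted as non-significant: the log odds ratio has no finite estimate there. The chance of that is 0.933¹⁵ ≈ 35% with 15 placebo subjects and 0.933¹⁹ ≈ 27% with 19. Normal-approximation formulas at 30/15 give 43% (pooled) and 62% (unpooled). By the pooled formula, 80% power needs 96 subjects (64 + 32), or 114 with continuity correction.

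**Step 4. Sensitivity to the placebo mean, difference held at 20, 30/15 (Fisher to likelihood ratio).**

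| Placebo mean | Power |
|---|---|
| +5 | 22–50% |
| 0 | 39–54% |
| −5 | 50–61% |
| −10 | 56–67% |
| −20 | 63–70% |

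Over placebo means from −40 to +40 the maximum is 71%, near −26. At 37/19, power reaches about 80% only with placebo means around −15 to −20, which put the inclisiran mean at −35 to −40.

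**Step 5. Sensitivity to the true difference, placebo mean 0.** A 25-point difference gives 67–76% at 30/15 and 77–85% at 37/19. Power of 80% needs a difference of about 26 to 28 points at 30/15, and about 24 to 26 at 37/19.

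**Step 6. Effect on the gate.** In 200,000 simulated trials per sample size, the primary and responder nulls were both rejected in 38/48/52% at 30/15 and 51/57/62% at 37/19 (Fisher/score/likelihood ratio). These are upper limits, because the other four key secondaries must also be rejected.

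**The case against.** The sample size is a minimum and 56 were enrolled, so power at 45 understates the actual trial. This stands as a matter of degree: at 37/19, non-significance is expected in 37–49% of trials (1 − 0.63 and 1 − 0.511), against 46–61% at 30/15. It does not rescue the claim.

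The hypothesis is a difference greater than 20, so a larger true effect is allowed, and at 25 points the enrolled trial has 77–85%. That is correct. But section 10.1 claims power to detect 20. The four-subject pilot in the same disease (section 1.2.2.2.3) showed a mean reduction of 21.0% at Day 180, which gives no reason to plan on much more.

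Normality and a zero placebo mean are not in section 10.1, and the protocol sets no numeric power target for key secondaries. Both points are fair. The 39–54% range depends on the first two, but at 30/15 with a 20-point difference no placebo mean brings power to 80%, the level the protocol uses for its primary.

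The protocol names logistic regression, not Fisher or score tests. Pooled odds ratios and confidence intervals would most naturally be Wald-type, which makes the power worse.

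Finally, the practical loss at the gate is small. For the other secondary endpoints section 10.4.3.2 says that "generally descriptive and graphical summaries by treatment group will be presented for the ITT population". That limits the consequence and not the error.

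**Conclusion.** The statement is wrong for the ≥30% responder endpoint at the planned effect and sample size. The primary has about 87% power at 30/15. The responder endpoint has about 39–54%, rising to 51–63% at 37/19, assuming normal percent changes, placebo mean 0, SD 20, a 20-point difference and no dropout. The range runs from Fisher to likelihood ratio; Wald inference falls well below it.

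The conclusion covers this endpoint only. The four continuous key secondaries cannot be checked, because the protocol gives no effect size or SD for Apo-B, non-HDL-C, total cholesterol or absolute LDL-C change. The claim for them is unsupported, not shown to be false.

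This should be corrected, but it does not affect the primary conclusion or any planned analysis.

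**What to change.** In section 10.4.3 and in the synopsis, limit the power statement to the primary endpoint (about 87% at 30/15). Add that, under the planning values with normality and placebo mean 0 assumed, the ≥30% responder endpoint has roughly 40–55% power at 45 subjects and about 50–63% at the 56 enrolled (Fisher to likelihood ratio, lower with a Wald test). Add also that a non-significant responder result is not evidence of no effect.

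Leave the testing rule and the gate as they are. Amendment 1 records that Part 1 ended "when the last subject completed the Day 180 visit and treatment allocation was unblinded", before this version was written, so any change to the rule would have to be labelled as made after unblinding.

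The cost is wording in two places and a less favourable power statement. No analysis changes and no extra patients are needed.
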